5.1.2 Participant Exclusion Criteria

Participants are excluded from the study if any of the following criteria apply:

1. A WOCBP who has a positive urine pregnancy test within 72 hours prior to study treatment start (see Appendix 3). If the urine test is positive or cannot be confirmed as negative, a serum pregnancy test will be required.
2. Has received prior therapy with an anti-PD-1, anti-PD-L1, or anti-PD-L2 agent or with an agent directed to another stimulatory or co-inhibitory T-cell receptor (eg, CTLA-4, OX-40, CD137).
3. Has received prior systemic anti-cancer therapy including investigational agents within 4 weeks prior to treatment start.

Note: Participants must have recovered from all AEs due to previous therapies to \leq Grade 1 or baseline. Participants with \leq Grade 2 neuropathy may be eligible.

Note: If participant received major surgery, they must have recovered adequately from the toxicity and/or complications from the intervention prior to starting study treatment.

4. Has received prior radiotherapy within 3 weeks of start of study treatment. Participants must have recovered from all radiation-related toxicities, not require corticosteroids, and not have had radiation pneumonitis. A 1-week washout is permitted for palliative radiation (\leq 2 weeks of radiotherapy) to non-CNS disease.
5. Has received a live vaccine within 30 days prior to the first dose of study drug. Examples of live vaccines include, but are not limited to, the following: measles, mumps, rubella, varicella/zoster (chicken pox), yellow fever, rabies, Bacillus Calmette–Guérin (BCG), and typhoid vaccine. Seasonal influenza vaccines for injection are generally killed virus vaccines and are allowed; however, intranasal influenza vaccines (eg, FluMist®) are live attenuated vaccines and are not allowed.
6. Is currently participating in or has participated in a study of an investigational agent or has used an investigational device within 4 weeks prior to the first dose of study treatment. Note: Participants who have entered the follow-up phase of an investigational study may participate as long as it has been 4 weeks after the last dose of the previous investigational agent.
7. Has a diagnosis of immunodeficiency (including organ grafts and HIV), or is receiving systemic steroid therapy (in dosing exceeding 10 mg daily of prednisone equivalent) or any other form of immunosuppressive therapy within 7 days prior to the first dose of study drug (exceptions: nasal corticosteroids, inhaled steroids, adrenal replacement steroids and steroid creams are allowed).
8. Has a known additional malignancy that is progressing or has required active treatment within the past 3 years. Note: Participants with basal cell carcinoma of the skin, squamous cell carcinoma of the skin, superficial bladder cancer or any carcinoma in situ (e.g. breast

carcinoma, cervical cancer in situ) that have undergone potentially curative therapy are not excluded.

9. Has known active CNS metastases and/or carcinomatous meningitis. Participants with previously treated brain metastases may participate provided they are radiologically stable, i.e. without evidence of progression for at least 4 weeks by repeat imaging (note that the repeat imaging should be performed during study screening), clinically stable and without requirement of steroid treatment for at least 14 days prior to first dose of study treatment.
10. Has severe hypersensitivity (\geq Grade 3) to pembrolizumab and/or any of its excipients.
11. Has active autoimmune disease that has required systemic treatment in the past 2 years (i.e. with use of disease modifying agents, corticosteroids or immunosuppressive drugs). Replacement therapy (eg. thyroxine, insulin, or physiologic corticosteroid replacement therapy for adrenal or pituitary insufficiency, etc.) is not considered a form of systemic treatment.
12. Has a history of (non-infectious) pneumonitis that required steroids or has current pneumonitis.
13. Has an active infection requiring systemic therapy.
14. Has a known history of Human Immunodeficiency Virus (HIV).
15. Has active infection with Hepatitis A (as determined by an acute hepatitis panel), a known history of Hepatitis B (Hepatitis B surface Ag reactive), or active Hepatitis C virus (qualitative HCV RNA detectable).
16. Active TB (Bacillus Tuberculosis) infection (as determined by Quantiferron Test).
17. Has a history or current evidence of any condition, therapy, or laboratory abnormality that might confound the results of the study, interfere with the subject's participation for the full duration of the study, or is not in the best interest of the subject to participate, in the opinion of the treating investigator.
18. Has known psychiatric or substance abuse disorders that would interfere with cooperation with the requirements of the trial.
19. Is pregnant or breastfeeding, or expecting to conceive children within the projected duration of the study, starting with the screening visit through 120 days after the last dose of trial treatment.
20. Patients with a history of cardiac disease are excluded: myocardial infarction or arterial thromboembolic events within 6 months prior to baseline, severe or unstable angina, New York Heart Association Class III or IV disease, QTcB (corrected according to Bazett's formula) interval >470 msec, serious uncontrolled hypertension (systolic >150 and/or

diastolic >100 mm Hg). Baseline electrocardiography, echocardiography and assessment of serum troponin (I) are included in the screening exams. Subjects in whom these assays are abnormal (EKG excluding 1st degree branch block, sinus bradycardia, sinus tachycardia or non-specific T wave changes, serum troponin \geq grade 2) are ineligible.

21. Patients with a family history or Li-Fraumeni syndrome will not be eligible.

22. History of severe environmental allergies or allergy to egg proteins.

5.1.3 Lifestyle Restrictions

5.1.3.1 Meals and Dietary Restrictions

Participants should maintain a normal diet unless modifications are required to manage an AE such as diarrhea, nausea or vomiting.

5.1.3.2 Contraception

Pembrolizumab may have adverse effects on a fetus in utero. Refer to Appendix 3 for approved methods of contraception.

5.1.4 Pregnancy

5.1.4.1 Female participants:

Pregnancies and suspected pregnancies (including a positive pregnancy test regardless of age or disease state) of a female participant occurring after the participant receives the first dose of protocol therapy up to 120 days post-last dose of pembrolizumab are considered immediately reportable events or 30 days following cessation of treatment if the subject initiates new anticancer therapy, whichever is earlier. **Protocol therapy is to be discontinued immediately. The pregnancy, suspected pregnancy, or positive pregnancy test must be reported to the Study PI and the DCC immediately within 24 hours of awareness.** The female subject may be referred to an obstetrician-gynecologist (preferably one with reproductive toxicity experience) or another appropriate healthcare professional for further evaluation.

The Investigator should make every effort to follow the female participant until completion of the pregnancy per institutional policies, and should notify the Study PI.

Abnormal pregnancy outcomes and neonatal deaths that occur within 28 days of birth should be reported as an SAE per expedited reporting guidelines.

If a participant inadvertently becomes pregnant while on treatment with pembrolizumab, the participant will be immediately discontinued from study treatment. The site will contact the participant at least monthly and document the participant's status until the pregnancy has been completed or terminated. The outcome of the pregnancy will be reported to Merck within 2 working days if the outcome is a serious adverse experience (eg, death, abortion, congenital anomaly, or other disabling or life-threatening complication to the mother or newborn). The study

Investigator will make every effort to obtain permission to follow the outcome of the pregnancy and report the condition of the fetus or newborn to Merck.

5.1.4.1.1 Use in Nursing Women

It is unknown whether pembrolizumab is excreted in human milk. Since many drugs are excreted in human milk, and because of the potential for serious adverse reactions in the nursing infant, participants who are breast-feeding are not eligible for enrollment. **The Sponsor must report any potential infant exposure through lactation within 10 calendar days of sponsor's awareness to Merck.**

5.1.4.2 Male participants:

If a female partner of a male participant becomes pregnant within 120 days post last dose of pembrolizumab, the male participant should notify the Investigator, and the pregnant female partner should be advised to call their healthcare provider immediately.

The Investigator should make every effort to follow the outcome of the pregnancy per institutional policies and should notify the Study PI.

5.2 Trial Treatments

The treatment to be used in this trial is outlined below in Table 2.

Table 1 Trial Treatment

Drug	Dose/Potency	Dose Frequency	Route of Administration	Regimen/Treatment Period	Use
Pembrolizumab	200 mg	Q3W	IV infusion	Day 1 of each 3 week cycle	Experimental
p53MVA	5.0×10^8 pfu	Q3W	injection into subcutaneous tissue of the upper arm (over deltoid muscle)	every 3 weeks for a total of 3 vaccinations	Experimental

5.2.1 Timing of Dose Administration

Trial treatment should be administered on Day 1 of each cycle after all procedures/assessments have been completed as detailed on the Trial Flow Chart (Section 6.0). Trial treatment may be administered up to 5 days before or after the scheduled Day 1 of each cycle due to administrative reasons. All trial treatments will be administered on an outpatient basis. Pembrolizumab 200 mg will be administered as a 30 minute IV infusion every 3 weeks. Sites should make every effort to target infusion timing to be as close to 30 minutes as possible. However, given the variability of

infusion pumps from site to site, a window of -5 minutes and +10 minutes is permitted (i.e., infusion time is 30 minutes: -5 min/+10 min). The Merck Pharmacy Manual contains specific instructions for the preparation of the pembrolizumab infusion fluid and administration of infusion solution. Section 9.0 of this protocol contains instructions for preparation and handling of the p53MVA vaccine.

5.2.2 Dose Modification and toxicity management for immune-related AEs associated with pembrolizumab

AEs associated with pembrolizumab exposure may represent an immunologic etiology. These immune-related AEs (irAEs) may occur shortly after the first dose or several months after the last dose of pembrolizumab treatment and may affect more than one body system simultaneously. Therefore, early recognition and initiation of treatment is critical to reduce complications. Based on existing clinical study data, most irAEs were reversible and could be managed with interruptions of pembrolizumab, administration of corticosteroids and/or other supportive care. For suspected irAEs, ensure adequate evaluation to confirm etiology or exclude other causes. In order to monitor for immune mediated hyperthyroidism and hypothyroidism, patients will be assessed for thyroid function (TSH) at baseline. TSH testing will be repeated during/after the treatment phase if clinical signs and symptoms of thyroid disorders are observed. Additional procedures or tests such as bronchoscopy, endoscopy, skin biopsy may be included as part of the evaluation. Based on the severity of irAEs, withhold or permanently discontinue pembrolizumab and administer corticosteroids. Dose modification and toxicity management guidelines for irAEs associated with pembrolizumab are provided in Table 3.

Table 3 Dose modification and toxicity management guidelines for immune-related AEs associated with pembrolizumab

General instructions:				
Immune-related AEs	Toxicity grade or conditions (CTCAEv5.0)	Action taken to pembrolizumab	irAE management with corticosteroid and/or other therapies	Monitor and follow-up
Pneumonitis	Grade 2	Withhold	
 Administer corticosteroids (initial dose of 1-2 mg/kg prednisone or equivalent) followed by taper 	
 Monitor participants for signs and symptoms of pneumonitis Evaluate participants with suspected pneumonitis with radiographic imaging and initiate corticosteroid treatment Add prophylactic antibiotics for opportunistic infections
	Grade 3 or 4, or recurrent Grade 2	Permanently discontinue		
Diarrhea / Colitis	Grade 2 or 3	Withhold	
 Administer corticosteroids (initial dose of 1-2 mg/kg prednisone or equivalent) followed by taper 	
 Monitor participants for signs and symptoms of enterocolitis (ie, diarrhea, abdominal pain, blood or mucus in stool with or without fever) and of bowel perforation (ie, peritoneal signs and ileus). Participants with \geq Grade 2 diarrhea suspecting colitis should consider GI consultation and

	Grade 4	Permanently discontinue		
 • performing endoscopy to rule out colitis. • Participants with diarrhea/colitis should be advised to drink liberal quantities of clear fluids. If sufficient oral fluid intake is not feasible, fluid and electrolytes should be substituted via IV infusion.
AST / ALT elevation or Increased bilirubin	Grade 2	Withhold	
 • Administer corticosteroids (initial dose of 0.5- 1 mg/kg prednisone or equivalent) followed by taper 	
 • Monitor with liver function tests (consider weekly or more frequently until liver enzyme value returned to baseline or is stable
	Grade 3 or 4	Permanently discontinue	
 • Administer corticosteroids (initial dose of 1-2 mg/kg prednisone or equivalent) followed by taper 	
Type 1 diabetes mellitus (T1DM) or Hyperglycemia	Newly onset T1DM or Grade 3 or 4 hyperglycemia associated with evidence of β -cell failure	Withhold	
 • Initiate insulin replacement therapy for participants with T1DM • Administer anti-hyperglycemic in participants with hyperglycemia 	
 • Monitor participants for hyperglycemia or other signs and symptoms of diabetes.
Hypophysitis	Grade 2	Withhold	
 • Administer corticosteroids and initiate hormonal replacements as clinically indicated. 	
 • Monitor for signs and symptoms of hypophysitis (including hypopituitarism and adrenal insufficiency)
	Grade 3 or 4	Withhold or permanently discontinue ¹		
Hyperthyroidism	Grade 2	Continue	
 • Treat with non-selective beta-blockers (eg, propranolol) or thionamides as appropriate 	
 • Monitor for signs and symptoms of thyroid disorders.
	Grade 3 or 4	Withhold or permanently discontinue ¹		
Hypothyroidism	Grade 2-4	Continue	
 • Initiate thyroid replacement hormones (eg, levothyroxine or 	
 • Monitor for signs and symptoms of thyroid disorders.

			liothyroinine) per standard of care	
Nephritis and Renal dysfunction	Grade 2	Withhold	
 Administer corticosteroids (prednisone 1-2 mg/kg or equivalent) followed by taper. 	
 Monitor changes of renal function
	Grade 3 or 4	Permanently discontinue		
Myocarditis	Grade 1 or 2	Withhold	
 Based on severity of AE administer corticosteroids 	
 Ensure adequate evaluation to confirm etiology and/or exclude other causes
	Grade 3 or 4	Permanently discontinue		
All other immune-related AEs	Intolerable/persistent Grade 2	Withhold	
 Based on type and severity of AE administer corticosteroids 	
 Ensure adequate evaluation to confirm etiology and/or exclude other causes
	Grade 3	Withhold or discontinue based on the type of event. Events that require discontinuation include and not limited to: Guillain-Barre Syndrome, encephalitis		
	Grade 4 or recurrent Grade 3	Permanently discontinue		

 Withhold or permanently discontinue pembrolizumab is at the discretion of the investigator or treating physician. 
NOTE: For participants with Grade 3 or 4 immune-related endocrinopathy where withhold of pembrolizumab is required, pembrolizumab may be resumed when AE resolves to \leq Grade 2 and is controlled with hormonal replacement therapy or achieved metabolic control (in case of T1DM).
				

Dose modification and toxicity management of infusion-reactions related to pembrolizumab

Pembrolizumab may cause severe or life-threatening infusion-reactions including severe hypersensitivity or anaphylaxis. Signs and symptoms usually develop during or shortly after drug infusion and generally resolve completely within 24 hours of completion of infusion. Dose modification and toxicity management guidelines on pembrolizumab associated infusion reaction are provided in Table 4.

Table 4A Pembrolizumab Infusion Reaction Dose modification and Treatment Guidelines

NCI CTCAE Grade	Treatment	Premedication at Subsequent Dosing
Grade 1 Mild reaction; infusion interruption not indicated; intervention not indicated	Increase monitoring of vital signs as medically indicated until the participant is deemed medically stable in the opinion of the investigator.	
Grade 2 Requires therapy or infusion interruption but responds promptly to symptomatic treatment (e.g., antihistamines, NSAIDs, narcotics, IV fluids); prophylactic medications indicated for ≤ 24 hrs	
Stop Infusion.
 
Additional appropriate medical therapy may include but is not limited to:
 
IV fluids Antihistamines NSAIDs Acetaminophen Narcotics
 
Increase monitoring of vital signs as medically indicated until the participant is deemed medically stable in the opinion of the investigator.
 
If symptoms resolve within 1 hour of stopping drug infusion, the infusion may be restarted at 50% of the original infusion rate (e.g. from 100 mL/hr to 50 mL/hr). Otherwise dosing will be held until symptoms resolve and the participant should be premedicated for the next scheduled dose.
 
Participants who develop Grade 2 toxicity despite adequate premedication should be permanently discontinued from further study drug treatment
	
Participant may be premedicated 1.5h (± 30 minutes) prior to infusion of _____ with: Diphenhydramine 50 mg po (or equivalent dose of antihistamine). Acetaminophen 500-1000 mg po (or equivalent dose of analgesic).

Grades 3 or 4 Grade 3: Prolonged (i.e., not rapidly responsive to symptomatic medication and/or brief interruption of infusion); recurrence of symptoms following initial improvement; hospitalization indicated for other clinical sequelae (e.g., renal impairment, pulmonary infiltrates) Grade 4: Life-threatening; pressor or ventilatory support indicated	
Stop Infusion.
 
Additional appropriate medical therapy may include but is not limited to:
 
Epinephrine** IV fluids Antihistamines NSAIDs Acetaminophen Narcotics Oxygen Pressors Corticosteroids
 
Increase monitoring of vital signs as medically indicated until the participant is deemed medically stable in the opinion of the investigator.
 
Hospitalization may be indicated.
 
**In cases of anaphylaxis, epinephrine should be used immediately.
 
Participant is permanently discontinued from further study drug treatment.
	No subsequent dosing
Appropriate resuscitation equipment should be available at the bedside and a physician readily available during the period of drug administration. For further information, please refer to the Common Terminology Criteria for Adverse Events v5.0 (CTCAE) at http://ctep.cancer.gov		

Other allowed dose interruption for pembrolizumab

Pembrolizumab may be interrupted for situations other than treatment-related AEs such as medical / surgical events or logistical reasons not related to study therapy. Participants should be placed back on study therapy within 3 weeks of the scheduled interruption, unless otherwise discussed with the Sponsor. The reason for interruption should be documented in the patient's study record.

Precautions and Dose modification and toxicity management of reactions related to p53MVA vaccine

Precautions: All subjects will be monitored for one hour in the clinic after each immunization. Notation will be made of the subject's temperature and of any local reaction at the injection site. The subjects will be contacted by telephone or e-mail approximately 24 and 48 hours after each immunization to evaluate vaccine related complications. If there is any clinical evidence to suggest myopericarditis, patients will receive a full cardiac evaluation, including EKG, serial troponins, echocardiography and consultation by a cardiologist. p53MVA vaccination will be withheld in patients showing \geq Grade 2 hepatitis.

Dose Reductions: In the first-in-human, single agent study, p53MVA vaccination was well-tolerated in 9 patients receiving a dose of 5.6×10^8 pfu. The highest level AE recorded was grade 2. Hence, we do not anticipate the need for p53MVA dose reductions. However if required, intra-patient dose reductions will be carried out as follows:

Table 4B p53MVA Vaccine Dose modification and Treatment Guidelines

Toxicity	Management
Grade ≥ 2 hepatitis related or unrelated to p53MVA Grade ≥ 3 allergic reactions possibly related to p53MVA	Skip and follow the patient weekly or as needed until the toxicity improves to $<$ Grade 2. May resume p53MVA in the next cycle at 2.8×10^8 pfu
Grade 3 non- hematologic toxicity, unrelated to p53MVA	Skip and follow the patient weekly or as needed until the toxicity improves to $<$ Grade 2. Resume p53MVA at 2.8×10^8 pfu
Grade 4 non- hematologic toxicity (even if unrelated to p53MVA)	Cease all study agents

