More encouraging results were achieved with the anti-PD-1 antibody, Nivolumab. Twenty patients with platinum-resistant ovarian cancer were treated with an intravenous infusion of nivolumab every 2 weeks at a dose of 1 or 3 mg/kg. The best overall response was 15%, which included two patients with durable complete responses (in the 3-mg/kg cohort). The disease control rate in all 20 patients was 45%, median PFS was 3.5 months (95% CI, 1.7 to 3.9 months) and median OS was 20.0 months (95% CI, 7.0 months to not reached) at study termination. However, grade 3 and higher AEs were observed in around 40% of patients [28].

Another ongoing study of PD-1 blockade in ovarian cancer combines Pembrolizumab with weekly paclitaxel (NCT02440425). Paclitaxel induces proinflammatory cytokine secretion and immune cell activation[50]. Another study of Pembrolizumab in ovarian cancer (NCT02054806) reported the following at ASCO 2015: of 26 patients treated, there was one complete response, 2 partial responses and 6 patients with stable disease[51].

This study will evaluate the p53MVA vaccine in combination with a checkpoint inhibitor, pembrolizumab. Subjects must have recurrent, platinum refractory ovarian cancer, with evidence of p53 over expression to be eligible. Patients will receive injections of p53MVA vaccine, for a total of three injections. Patients will be evaluated for toxicity through the first cycle of therapy.

Pembrolizumab will be administered at a standard dose of 200 mg every 3 weeks, for approximately two years (35 cycles). In the case of grade 3 vaccine related toxicity, the dose of p53MVA will be decreased. In the case of pembrolizumab induced immune-mediated adverse events, treatment will be held or permanently discontinued according to the package insert. Pembrolizumab treatment may be extended beyond 49 weeks (17 cycles) if a second course is indicated (see Section 5.2.3). This study will be conducted in compliance with the protocol, Good Clinical Practice (GCP) and the applicable regulatory requirements.

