5.4 Participant Withdrawal/Discontinuation Criteria

Participants may discontinue study treatment at any time for any reason or be dropped from the study treatment at the discretion of the investigator should any untoward effect occur. In addition, a participant may be discontinued from study treatment by the investigator or the Sponsor if study treatment is inappropriate, the trial plan is violated, or for administrative and/or other safety reasons. Specific details regarding procedures to be performed at study treatment discontinuation are provided in Section 7.1.4 – Other Procedures.

A participant must be discontinued from study treatment but continue to be monitored in the study for any of the following reasons:

- The participant or participant's legally acceptable representative requests to discontinue study treatment
- Confirmed radiographic disease progression, according to irRECIST criteria (outlined in Section 7.1.2.6)
- Any progression or recurrence of any malignancy, or any occurrence of another malignancy that requires active treatment
- Unacceptable adverse experiences as described in Section 5.2.2.
- The participant has a medical condition or personal circumstance which, in the opinion of the investigator and/or sponsor, placed the participant at unnecessary risk from continued administration of study treatment.
- The participant has a confirmed positive serum pregnancy test
- Noncompliance with study treatment or procedure requirements
- Recurrent Grade 2 pneumonitis
- Discontinuation of treatment may be considered for participants who have attained a confirmed complete response (CR), at the PI's discretion. These participants may be eligible for second course treatment described in Section 5.2.3.
- The participant is lost to follow-up
- Completion of 35 treatments with pembrolizumab

Note: The number of treatments is calculated starting with the first dose. Participants who stop will stop pembrolizumab after receiving 17 doses on study. Patients may be eligible for retreatment if they progress after stopping study treatment provided they meet the requirements detailed in Section 5.2.3. Participants may be retreated in the Second Course Phase (Retreatment) for up to an additional 17 cycles (approximately 1 year).

- Administrative reasons

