7.2.8 Assessment of Adverse Events

The PI will be responsible for determining the event name, and assessing the severity (i.e. grade), expectedness, and attribution of all adverse events as applicable per the City of Hope Clinical Research Adverse Event and Unanticipated Problem policy. Adverse events will be characterized using the descriptions and grading scales found in NCI CTCAE v5.0. A copy of the scale can be found at:

https://ctep.cancer.gov/protocoldevelopment/electronic_applications/ctc.htm.

The following definitions will be used to determine the causality (attribution) of the event to the study agent or study procedure.

- **Unrelated** – The event is clearly NOT related to study treatment, and is clearly related to other factors such as the participant's clinical state, other therapeutic interventions, or concomitant medications administered to the participant.
- **Unlikely** – The event is unlikely related to the study treatment, and is most likely related to other factors such as the participant's clinical state, other therapeutic interventions, or concomitant drugs.
- **Possible** – The event may be related to study treatment, as it follows a reasonable temporal sequence from the time of drug administration, but could have been produced by other factors such as the participant's clinical state, other therapeutic interventions, or concomitant drugs.
- **Probable** – The event is most likely related to the study treatment, as it follows a reasonable temporal sequence from the time of drug administration and a known response pattern to the study drug, and is unlikely related to the participant's clinical state, other therapeutic interventions, or concomitant drugs.
- **Definite** – The event is clearly related to the study treatment, as it follows a reasonable temporal sequence from the time of drug administration and a known response pattern to the study drug, and is not reasonably explained by other factors such as the participant's condition, therapeutic interventions, or concomitant drugs.

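### Table 4B directs p53MVA to resume after Grade 3 toxicity unrelated to the vaccine and does not except immune events that permanently stop pembrolizumab, in conflict with Section 5.4

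*Combined protocol and SAP*

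**What the plan says.** Section 5.2.2 carries separate rules for the two agents.

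- **Table 3 (pembrolizumab).** Pembrolizumab is permanently discontinued for Grade 3 myocarditis, Grade 3 nephritis and Grade 3 pneumonitis (the pneumonitis trigger reads "Grade 3 or 4, or recurrent Grade 2"). The row for all other immune-related events adds: "Events that require discontinuation include and not limited to: Guillain-Barre Syndrome, encephalitis". The action column addresses pembrolizumab only.
- **Table 4B (p53MVA).** The trigger of the middle row is "Grade 3 non- hematologic toxicity, unrelated to p53MVA". The action is to skip the vaccine, follow the patient until the event is below Grade 2, and then resume at 2.8 × 10^8 pfu. The row excepts no type of event and does not refer to Table 3. The last row ceases all study agents for Grade 4 non-hematologic toxicity, whatever the attribution.
- **Section 5.4.** Study treatment must be discontinued for "Unacceptable adverse experiences as described in Section 5.2.2", for recurrent Grade 2 pneumonitis, and for a medical condition that, in the investigator's or sponsor's opinion, puts the participant at unnecessary risk.
- **Section 4.2.1.** "In the case of grade 3 vaccine related toxicity, the dose of p53MVA will be decreased".

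The vaccine precautions in Section 5.2.2 also order a full cardiac work-up with a cardiology consultation when myopericarditis is suspected. They do not say what happens to the next vaccine dose in the meantime.

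**The concern.** Take a patient with Grade 3 immune-related myocarditis or pneumonitis after the first or second combined dose, attributed to pembrolizumab. Table 3 ends pembrolizumab for good. Once the event is at Grade 1, Table 4B tells the investigator to give the vaccine again, possibly with residual disease. Section 5.4 can be read to say the opposite.

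Three features of the protocol make resumption hard to justify in such a patient:

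- Section 5.2.2 says that immune-related events can appear months after pembrolizumab has ended, so stopping it does not remove the immune risk at once.
- Pembrolizumab is given in order to strengthen the vaccine's activity (Sections 2.1 and 7.1.5.2).
- The eligibility rules in Section 5.1.2 exclude a history of non-infectious pneumonitis that needed steroids, and abnormal cardiac screening tests.

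What is at stake is the safety of an individual patient and consistent handling by investigators. Nothing here bears on the response-rate design in Section 8.2.

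**Working it through.** The plan states no figure on this point, so the check sets the rules side by side and then bounds the exposure.

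**1. Events that meet both rules.** These are Grade 3 events for which Table 3 requires, without discretion, a permanent stop of pembrolizumab, and which fall in Table 4B's Grade 3 row if judged unrelated to the vaccine:

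| Grade 3 event | Pembrolizumab (Table 3) | p53MVA (Table 4B) |
|---|---|---|
| Pneumonitis | permanent stop | skip, then resume |
| Nephritis / renal dysfunction | permanent stop | skip, then resume |
| Myocarditis | permanent stop | skip, then resume |
| Guillain-Barré syndrome | permanent stop | skip, then resume |
| Encephalitis | permanent stop | skip, then resume |

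That gives 3 rows of their own + 2 named under other events = 5. Endocrine events are left out because stopping is discretionary. Grade 3 diarrhea or colitis is left out because pembrolizumab is only withheld. Liver events are left out because, if recorded as hepatitis, they fall in a different and permissive row.

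**2. How an event reaches the row.** Section 5.3.3 applies the Table 3 guidance when the investigator judges the event related to pembrolizumab. Attribution to that agent and not to the vaccine is the route into the row. Section 7.2.8 sets a high bar for calling an event unrelated: "The event is clearly NOT related to study treatment", with another clear cause.

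**3. If the event is attributed to the vaccine.** Table 4B then has no general Grade 3 row, and Section 4.2.1 calls only for a lower dose. The word *unrelated* in the row may therefore be a drafting slip. If *related* was meant, the row would still lack the exception.

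**4. Section 5.4 against Table 4B.** Section 5.2 lists both agents as trial treatment, so study treatment in Section 5.4 is read here as both. Section 5.2.2 does not define *unacceptable* for p53MVA. If the term covers the five events, Section 5.4 says stop where Table 4B says resume. If it does not, the stop depends on the unnecessary-risk clause, which asks the investigator to override an explicit instruction. Section 5.4 also stops study treatment for recurrent Grade 2 pneumonitis, whereas Table 4B would resume the vaccine after a Grade 3 episode.

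**5. Exposure window.** Vaccine is given at weeks 1, 4 and 7 (Section 7.1.5.2).

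- Doses that can follow an on-treatment event: 3 − 1 = 2 (doses 2 and 3).
- Week 1 day 1 to week 7 day 1: 6 × 7 = 42 days.
- With one permitted adverse-event delay of under 3 weeks: under 42 + 21 = 63 days, or 9 weeks.

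The ±5-day visit window is ignored, and skipped doses are assumed not to be added after week 7. The event must begin, reach Grade 3 and fall below Grade 2 inside that window.

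**The case against.** The case on the other side is substantial.

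- **Attribution.** Under the Section 7.2.8 definition it is hard to call myocarditis clearly unrelated to a vaccine given at the same visit as pembrolizumab, in a protocol that itself looks for myopericarditis after vaccination. This stands, and it narrows the case. It has less force for the other four events.
- **Section 5.4 already stops the vaccine.** The unnecessary-risk clause is mandatory once the investigator or sponsor forms that opinion. This stands as a safeguard. A reader might infer that nothing could stop the vaccine; the documents do not support that. The defect is that the table points the other way.
- **No vaccine-only regimen is described.** Both agents are given together, pembrolizumab first, and only pembrolizumab is provided for alone. That suggests vaccination after a permanent stop was not intended, but Table 4B does not say so.
- **Prior safety.** Section 5.2.2 reports nothing above Grade 2 in 9 patients at 5.6 × 10^8 pfu of vaccine alone, and Section 7.3.4 expects no overlapping toxicity. This supports rarity, not the instruction.

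Three stronger readings are tempting and should not be used. First, the row covering "hepatitis related or unrelated to p53MVA" might be taken as the same error, but it only permits resumption, so it does not conflict with Section 5.4. Second, the troponin schedule might be read as leaving dose 3 unchecked, but the flow chart's columns are scrambled in the available text. Third, the unstated hold for suspected myopericarditis might look like an equal defect. It is closer to missing detail, because a full cardiac work-up and consultation are ordered and doses are three weeks apart.

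**Conclusion.** The point holds in a narrow form. Table 4B's directive to resume p53MVA after an unrelated Grade 3 event lacks an exception for five named immune events that end pembrolizumab, and it is at odds with Section 5.4. It can affect at most doses 2 and 3, within about 6 weeks of the first dose (under 9 with one delay), and only at Grade 3.

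The situation should be rare. The documents do not allow its frequency to be estimated, and they show no harm from giving p53MVA after a resolved pembrolizumab event. The case for acting is that the possible event is serious and the correction is small.

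The conclusion assumes that study treatment in Section 5.4 means both agents. It also assumes that the general-instructions cell of Table 3, blank in the available text, holds no rule for the vaccine. If it does hold one, Table 4B would still need to agree with it.

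**What to change.** Amend Table 4B in two places:

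1. Add a sentence that p53MVA is permanently stopped when pembrolizumab is permanently discontinued for an immune-related event.
2. Limit the instruction to resume in the Grade 3 row to all other events, with a reference to Section 5.4.

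As a secondary clarification in the vaccine precautions, state that p53MVA is held while suspected myopericarditis is under the cardiac evaluation already required, and is not resumed after confirmed Grade 3 myocarditis.

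The cost is a short protocol amendment, with no added tests, patients or analyses. The downside is that a few patients may miss vaccine dose 2 or 3.
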